3.6 Pharmacokinetic Analysis

CSF and Plasma samples will be collected at protocol designated times for ISIS 814907 pharmacokinetic assessments from the dose cohorts. Only concentration data from patients randomized to receive study drug (ISIS 814907) will be included in this analysis. The PK analyses will be performed for the MAD Period and LTE Period separately according to the analysis groups given in Section 3.2.2.

3.6.1 CSF Concentration Data and Pharmacokinetics

A CSF sample will be collected pre-dose on each injection day in the MAD and LTE and during post-treatment evaluation periods in the MAD and LTE for PK analyses. CSF concentrations of ISIS 814907, along with the scheduled (nominal) and actual samples times (i.e., time from IT dosing) will be listed (when applicable) for each patient, analysis group, nominal dose, and day. Differences between scheduled and actual sampling days will also be listed for all patients, as well as percent differences between actual administered dose and nominal dose.

CSF concentrations below the lower limit of quantification (LLOQ) will be indicated by "BLQ". For the purpose of calculating typical descriptive statistics (n, mean, SD, %CV, geometric mean, geometric %CV, median, minimum, and maximum) for CSF concentrations, all BLQ values will be set to LLOQ/2 after the first active dose and will be set to 0 prior to the first active dose. Mean CSF concentrations that are BLQ will be presented as BLQ, and the SD and %CV will be reported as not applicable. Summary statistics of the ISIS 814907 CSF concentrations will be tabulated for the MAD and LTE Periods separately by analysis group, nominal dose and day. At the discretion of the pharmacokineticist and/or biostatistician, samples may be excluded from descriptive statistics if there are large deviations between scheduled and actual sampling days, or large deviations between actual dose and nominal dose.

The ISIS 814907 half-life in CSF will be calculated, if possible, for the MAD Period and summarized by analysis group, nominal dose, and nominal day.

ISIS 814907 CSF concentration versus time (actual) profiles from Day 1 to last collection, for each patient, as well as the mean (±SE) CSF concentration versus time (scheduled) profiles for each treatment cohort, will be presented graphically on linear scale for the MAD and LTE Periods separately. Samples may be excluded from the mean plots if there are large deviations between scheduled and actual sampling times, or large deviations between actual dose and nominal dose.

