Cohort D: N = 16, mild AD, 90 mg ISIS 814907 or placebo x 4 doses *or* 115 mg ISIS 814907 x 2 doses

The overall randomization ratio in each cohort is 3:1 ISIS 814907 to placebo.

Following the 3-month Treatment Evaluation Period, there will be a 6-month Post-Treatment Period.

3.1.2 Long-Term Extension, Part 2

The open-label LTE, Part 2, of the study will start with Cohort C and allow all patients in Cohorts C and D to seamlessly transition from Part 1 to Part 2. This means that for Cohorts C and D patients Day 253 in Part 1 will correspond to Day -1 in Part 2. In Part 2, the Treatment Evaluation Period of 48 weeks will be followed by a Post-Treatment Period of 16 weeks.

All patients will receive ISIS 814907 in Part 2 and will be dosed at an 84-day interval, regardless of the dose interval utilized in Part 1. Cohort C patients will continue the Cohort C dose with a quarterly (84-day) dose interval in the LTE, Part 2; Cohort D patients will continue the Cohort D dose with a quarterly (84-day) dose interval in the LTE, Part 2. Cohort A and B patients who have completed the Treatment Evaluation and Post-Treatment Periods in Part 1 are also eligible to enter Part 2 of the study. For Cohorts A and B patients there will be a variable gap of time between the end of Part 1 and entry into Part 2. There is no prescribed minimum or maximum interval of time required before Cohort A and B patients completing Part 1 can enter Part 2 of the study, however all Cohort A and B patients participating in the LTE, Part 2, should be enrolled in Part 2 prior to the last patient in Cohort D entering Part 2 of the study. Patients who participated in Cohorts A and B will be able to start the LTE, Part 2 of the study at the Cohort C dose with a quarterly (84-day) dose interval, if permitted by the FSMG review of the Cohort C package for the dose-escalation meeting to Cohort D (2/3 of patients in Cohort C having received all doses of Study Drug in Part 1). Patients entering the LTE Part 2 will be maintained on the dose they received when they initiated Part 2. Dose levels and dosing regimen in the LTE, Part 2 could be adjusted in individuals or for the entire study based on ongoing review of the safety, PK/PD

profile by the FSMG and the Sponsor. In the LTE, Part 2, the Treatment Evaluation Period of 48 weeks will be followed by a Post-Treatment Period of 16 weeks.

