Appendix A Schedule of Procedures – MAD Part 1, all Cohorts Continued

- 4 APP, PSEN1, PSEN2, APOE, BCHE, IL1RAP and MAPT H1 haplotype (unless tested previously and laboratory report is available for documentation)
- 5 Height measured at Screening only
- Full physical and neurological exam (including fundi) to be given at Screening and abbreviated physical (but full neurological) exam to be given during treatment and follow-up period as indicated to assess changes from Screening. In addition to administration on the visits shown, neurological exam should be conducted if patient experiences an adverse event suggestive of cognitive or motor dysfunction
- 7 Measured in triplicate at the Day 1 visit (pre-dose only)
- 8 Women who are not surgically sterile
- 9 In addition to administration on the visits shown, RBANS and MMSE should be administered if the patient experiences an adverse event suggestive of cognitive or motor dysfunction
- 10 Stored at -80 °C for follow-up exploration of laboratory findings and/or adverse events (e.g., measurement of cytokine and/or chemokine levels, measurement of additional markers of kidney function, measurement of antibodies) in this or subsequent clinical studies of ISIS 814907
- 11 Local laboratory analysis of PT, INR, aPTT, and platelets must be conducted, and results reviewed prior to performing any LP on the next day during the Treatment Evaluation Period or the same day during the Post-Treatment Period. At Screening, analysis of PT, INR, aPTT, and platelets must be conducted and results reviewed within 2 days prior to the Screening LP
- 12 Local analysis of PT, INR, aPTT, and platelets is only conducted at Day 253 (Week 37) in patients who will undergo CSF sampling at this visit if they missed a previous LP during the study
- 13 CSF sampling will be conducted at Day 253 (Week 37) as part of the ET procedures in only those patients who did not complete all previous CSF samplings in the study
- 14 Each patient will undergo PET imaging with either FDG or Tau. FDG-PET will be performed unless Tau-PET is available and has been approved at the site. As soon as Tau-PET is approved and available at a site, patients should switch to Tau-PET imaging, instead of FDG-PET imaging, for their next scan

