1.3.2 Pharmacokinetic Endpoints

CSF samples are collected pre-dose on each injection day during the treatment period:

- Part 1: Days 1, 29, 57, and 85 for the 4-dose regimen, or Days 1 and 85 for the 2-dose regimen.
- Part 2: Days 1, 85, 169, 253, 337.

CSF samples are also collected during the Post-Treatment Period:

- Part 1: Days 113 and 141 for patients in Cohorts A and B, and Days 141 and 197 for patients in Cohorts C and D
- Part 2: Day 421

Plasma samples will be collected for PK analyses on the following days:

Part 1: Days 1, 2, 29, 57, 85, and 86, during the Treatment Evaluation Period and on Days 113, 141, 169, 197 (patients in Cohorts C and D only) and 253 during the Post-Treatment Period

Part 2: Days 1, 2, 85, 169, 253, 337, and 338 during the Treatment Evaluation Period and on Days 421 and 449 during the Post-Treatment Period

Plasma post-distribution drug levels will be measured. C_{max} and area under the curve (AUC) will be determined, and elimination half-life will be assessed where appropriate.

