3.2.1 Analysis Periods

There are four periods which will be used for analysis and are defined as:

- MAD Period: Analyses include data from MAD, Part 1.
- LTE Period: Analyses include data from LTE, Part 2.
- MAD+LTE Period: Analyses include integrated data from both MAD, Part 1 and LTE, Part 2, regardless of a subject's randomization assignment or LTE enrollment status. For example, a subject receiving MAD placebo treatment who does not enroll in LTE will still contribute data from the MAD to this analysis.
- Active Treatment Period: Analyses include data from study periods in which a subject receives active ISIS 814907 treatment. (Note: Study periods refer to Part 1 and/or Part 2, including post-treatment follow-up but excluding any variable gaps in time between Part 1 and Part 2 for subjects in Cohorts A and B). Data collected during a placebo dosing period are not included (except relevant baseline data). Subjects who receive MAD active treatment will contribute data regardless of LTE enrollment status. Subjects who receive MAD placebo treatment will only contribute data if enrolled and dosed in the LTE.

In general, listings will be created for the MAD Period and the MAD+LTE Period.

Safety, pharmacodynamic and exploratory analyses will be conducted for the MAD Period and the LTE Period separately.

The MAD+LTE Period will be used to analyze select biomarkers, neuroimaging and key clinical assessments:

- o MRI (exploratory)
- o Tau-PET/FDG-PET
- o CSF biomarkers including but not limited to total tau, phospho-tau and A-beta42
- o MMSE
- o RBANS
- o CDR

The Active Treatment Period will be used to analyze select safety endpoints including:

- Laboratory assessments: Potential clinically significant laboratory abnormalities, hepatotoxicity, and shift analyses
- o CSF Safety Panel
- o Safety MRIs
- o Incidence rates for treatment emergent adverse events (TEAEs) and serious TEAEs

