3.4.3 Planned Interim Analysis

3.4.3.1 End of MAD, Part 1

An interim analysis of the MAD Period to investigate safety, PK, PD and exploratory endpoints will be conducted at the end of MAD, Part 1 when the last patient completes the last visit, and the results will be summarized by treatment group. Unblinded data will be evaluated at this analysis. All patients/all data through the end of MAD, Part 1 will be used for the analysis with the exception of CSF biomarkers data (through Day 1 pre-dose in LTE, Part 2). The individuals involved in the unblinded interim analysis will be identified and documented at the time of unblinded interim analysis according to Ionis standard operation procedure (SOP). The investigators, patients and study center personnel, including the site pharmacist, will be blinded to treatment assignment from the MAD for the duration of the study (i.e., until the end of LTE).

The MAD Period will be analyzed during this IA. The analysis of the LTE, MAD+LTE, and Active Treatment Periods will be performed following the final study lock after completion of the LTE period.

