3.7.1 Biochemical Analysis

Total tau in CSF is the key exploratory endpoint for the study. Other potential CSF biomarkers included in the analysis are target engagement (phospho-tau), A-beta42, A-beta40, total tau to A-beta42 ratio, A-beta42 to A-beta40 ratio, NfL, total NfH, neurogranin, YKL-40. If total tau to A-beta42 ratio is missing, but total tau and A-beta42 are available, then total tau to A-beta42 ratio will be derived as total tau divided by A-beta42. A-beta42 to A-beta40 ratio will be derived as A-beta42 divided by A-beta40.

In the MAD Period, the actual values, change, and percent change from baseline for CSF biomarkers at each visit will be summarized using descriptive statistics. CSF biomarkers at Day 1 (pre-dose) visit in the LTE will also be added in the MAD Period analysis. The absolute change and percent change from baseline for CSF biomarkers at each post-baseline visit will be compared between ISIS814907-treated groups and the pooled placebo group. The absolute changes from baseline at each post-baseline visit will be compared between each ISIS 814907 treated analysis group and pooled placebo using the ANCOVA with baseline value as covariate or Wilcoxon Rank Sum test, as appropriate. Since the percent change from baseline for biochemical data is not always normally distributed, an analysis of covariance (ANCOVA) model will be fit to the log-transformed data with treatment group as factors and log-transformed baseline value as covariate. The log-transformed data is obtained by taking the log of the ratio of post-baseline and baseline values, i.e., log (Y/X), where Y is the post-baseline value and X is the baseline value of biomarker. The model will provide an estimate of the log ratio \hat{c} , which will be converted back to the ratio scale. The percent change from baseline will then be estimated based

on the estimated ratio scale, that is $[\exp(\hat{c}) - 1] \times 100\%$. The results provide an overall estimate, with corresponding CIs and p-value.

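### SAP 3.6 limits the PK analysis to patients randomized to ISIS 814907, against the SAP's own PK Population and LTE groups; separately, a supplementary CSF half-life using the LTE Day 1 sample is worth considering

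*Combined protocol and SAP*

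**What the plan says.** **Who enters the PK analysis.**
- SAP 3.6 restricts it to concentration data from patients randomized to ISIS 814907. It then says "The PK analyses will be performed for the MAD Period and LTE Period separately", using the analysis groups of 3.2.2.
- SAP 3.4.1 defines the PK Population as randomized patients with at least one ISIS 814907 dose and sufficient sampling. It does not require randomization to the active arm.
- SAP 3.2.2.2 forms the LTE 60 mg and 115 mg groups from all roll-overs of the relevant cohorts, whatever they were randomized to. It lists PK among the uses of the 60 mg group. The All Roll-over group is expressly barred from PK; the Late Start (Part 1 placebo) groups are not.
- Protocol 10.3 defines its PK Population by randomization to ISIS 814907.

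**CSF half-life.**
- SAP 3.6.1: "The ISIS 814907 half-life in CSF will be calculated, if possible, for the MAD Period". SAP 3.2.1: "MAD Period: Analyses include data from MAD, Part 1".
- Part 1 post-treatment CSF samples are on "Days 113 and 141 for patients in Cohorts A and B, and Days 141 and 197 for patients in Cohorts C and D" (SAP 1.3.2). Day 253 is sampled only in "those patients who did not complete all previous CSF samplings in the study" (protocol Appendix A, footnote 13).
- A CSF PK sample is also drawn pre-dose on LTE Day 1 (SAP 1.3.2). For biomarkers, that visit is carried back: "CSF biomarkers at Day 1 (pre-dose) visit in the LTE will also be added in the MAD Period analysis" (SAP 3.7.1). The end-of-MAD data cut in 3.4.3.1 makes the same exception, for CSF biomarkers only.

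**The concern.** The sentence in 3.6 and the definitions in 3.4.1 and 3.2.2.2 cannot all be followed. Two programmers could produce different LTE PK tables, one with Part 1 placebo roll-overs and one without. Those patients matter for interpretation because their LTE concentrations carry no residue from Part 1 active dosing. CSF PK is the study's secondary objective.

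The half-life question is separate and smaller. In Cohorts C and D the LTE Day 1 pre-dose sample is in effect the last sample of the Part 1 washout, since no dose intervenes. The SAP treats it that way for biomarkers but not for the half-life. With two routine samples, a log-linear fit has no residual degrees of freedom and its shape cannot be checked.

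**Working it through.** **1. Counts.** The cohort sizes 8 + 8 + 12 + 16 = 44 reproduce the planned number. The first two patients in each cohort are allocated 1:1 and the rest 5:1, 5:1, 8:2 and 11:3.

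| Cohort | Active | Placebo |
|---|---|---|
| A | 1 + 5 = 6 | 1 + 1 = 2 |
| B | 1 + 5 = 6 | 1 + 1 = 2 |
| C | 1 + 8 = 9 | 1 + 2 = 3 |
| D | 1 + 11 = 12 | 1 + 3 = 4 |
| Total | 33 | 11 |

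Placebo roll-overs receive 60 mg if from A, B or C (2 + 2 + 3 = 7) and 115 mg if from D (4). These are planned maxima, because LTE entry may be lower. Under the literal 3.6 sentence, the LTE 60 mg PK group loses up to 7 of 28 and the 115 mg group up to 4 of 16. Both Late Start groups would be empty in the PK tables, although 3.6 itself points to the groups of 3.2.2.

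**2. Which reading the rest of the SAP supports.** The PK Population in 3.4.1, the PK use of the 60 mg group, and the absence of a PK bar on Late Start all include placebo roll-overs. The rule in 3.6.1 for CSF values below quantification is keyed to the first active dose, which also fits patients first dosed in the LTE. Only the 3.6 sentence, and protocol 10.3 behind it, points the other way.

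**3. Sampling times for half-life.** The last Part 1 dose is on Day 85 in both regimens.
- Cohorts A/B: Days 113 and 141, so 28 and 56 d after the last dose.
- Cohorts C/D: Days 141 and 197, so 56 and 112 d.
- In C/D, Part 1 Day 253 is LTE Day -1, so LTE Day 1 is nominally Day 254, and 254 − 85 = 169 d.

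**4. Precision per patient in C/D.** For a log-linear slope with constant log-scale error, SE = σ/√Sxx, where Sxx = Σ(t − mean t)².
- (56, 112): 28² + 28² = 1568.
- (56, 112, 169): 56.33² + 0.33² + 56.67² = 6384.7.
- √(6384.7/1568) = 2.02, so the SE about halves. Moving each visit by −7, 0 or +7 d gives 1.63 to 2.72. There is now one residual degree of freedom. This concerns up to 9 + 12 = 21 active patients.

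**5. Is the third sample quantifiable?** The 169-d level relative to the 56-d level is 2^(−113/T). For T = 20, 30, 60 and 120 d this is 2%, 7%, 27% and 52%. The documents give neither half-life nor LLOQ.

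**6. Effect on the group median.** Illustrative simulation: log-normal half-life (log-SD 0.30), residual log-SD 0.30, LLOQ as a share of the median 56-d level, third point used only if quantifiable, median of 12 reportable patients. All these values are assumptions.

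| True median, LLOQ | RMSE of median, two points | RMSE with third point |
|---|---|---|
| 20 d, 10% | 5.0 d | 5.8 d |
| 30 d, 10% | 5.4 d | 6.0 d |
| 30 d, 2% | 4.7 d | 3.5 d |
| 60 d, 10% | 14.1 d | 9.5 d |

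With a high LLOQ the third point is available mainly in slow eliminators. At 30 d and 10%, the median estimate is 32 d with two points and 34 d with the third.

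**7. If decline is not log-linear.** Suppose 90% of the initial level declines with a 10-d half-life and 10% with a 120-d half-life. The C/D estimate is then 71 d from two points and 89 d from three, while A/B's two points give 23 d, with no dose effect at all.

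**The case against.** On inclusion, the 3.6 sentence agrees with protocol 10.3, and a careful reader could recover the intent from 3.2.2 and 3.4.1. That makes the conflict easy to repair, but does not remove it: the explicit sentence in the PK section is the one a programmer would follow. A reader might infer that headline results are at risk. They are not. Part 1 placebo patients cannot contribute to the MAD half-life, and the key LTE correlation is specified in 3.7 on the ITT population.

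On half-life the opposing case is stronger, and most of it stands.
- The protocol synopsis places CSF half-life under Part 1, and protocol 10.6.3 names no period, so the SAP restriction is a defensible reading.
- A reader might infer that the LTE Day 1 concentration is discarded. It is not: 3.6.1 lists, tabulates and plots it in the LTE Period.
- 3.6.1 names no estimator, so the missing residual degree of freedom and the factor 2.02 apply only to a log-linear slope on post-last-dose samples.
- The SAP reports group summaries, and step 6 shows these can get worse as well as better.
- Extending only C/D widens the mismatch in washout windows with A/B. A/B cannot be aligned, because the gap before the LTE is open: "There is no prescribed minimum or maximum interval of time required before Cohort A and B patients completing Part 1 can enter Part 2".
- PK concentrations are held outside the EDC system (SAP 2.5.3). That LTE Day 1 CSF drug results would be ready at the interim cut is not established.

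A reader might therefore go further and replace the Part 1 half-life with a three-point estimate. The documents do not support that, since the direction of the effect depends on half-life and LLOQ, which they do not give.

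**Conclusion.** The inclusion sentence in SAP 3.6 is wrong as written. It contradicts 3.4.1 and 3.2.2.2 and, taken literally, drops up to 11 dosed patients (7 at 60 mg, 4 at 115 mg) from the LTE PK summaries. This rests on the text and the planned allocation alone.

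The half-life point is an optional improvement. The Part 1 restriction is consistent with the synopsis and should remain the main analysis. A supplementary estimate in C/D gains about a factor of two in per-patient slope precision, provided decline is log-linear to 169 d and the sample is quantifiable. Whether the reported median becomes more accurate is unknown. With or without the third point, A/B and C/D use different washout windows, so a difference between them should not be read as dose-dependence.

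**What to change.** **SAP 3.6 (needed).** Replace the restriction by randomized arm with one by exposure: patients who received ISIS 814907 in the analysis period. Record this as a departure from the protocol 10.3 PK Population. Cost: one sentence and a note. The MAD PK analysis is unchanged.

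**SAP 3.6.1 (optional).** Keep the Part 1 half-life as the main CSF estimate. For Part 1 active patients of Cohorts C and D who roll over, add a labelled supplementary estimate that includes the LTE Day 1 pre-dose concentration when it is quantifiable. Use actual times since the last Part 1 dose, keep LLOQ/2 values out of the slope, and report the number of points per patient. Show it beside the Part 1 estimate, with a caution against reading A/B versus C/D as a dose effect.

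The sample is already scheduled, so no visit or procedure is added. The cost is one more summary, with a number of points that varies between patients and no gain for those who do not roll over or fall below quantification. If the LTE Day 1 CSF drug results are not available at the end-of-MAD analysis, report the supplementary estimate at the final analysis.

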3.6.2 Plasma Concentration Data

Plasma concentrations of ISIS 814907, along with the scheduled (nominal) and actual samples times (i.e., time from IT dosing) will be listed (when applicable) for each patient, analysis group, nominal dose, and day. Percent differences between scheduled and actual sampling times will also be listed for all patients as well as percent differences between actual administered dose and nominal dose.

Plasma concentrations below the lower limit of quantification (LLOQ) will be indicated by "BLQ". For the purpose of calculating typical descriptive statistics (n, mean, SD, %CV, geometric mean, geometric %CV, median, minimum, and maximum) for plasma concentrations, all BLQ values will be set to LLOQ/2 with the exception of concentration prior to the first dose which will be set to '0'. Mean plasma concentrations that are BLQ will be presented as BLQ, and the SD and %CV will be reported as not applicable. Summary statistics of the ISIS 814907 plasma concentrations will be tabulated for the MAD and LTE periods separately by analysis group, nominal dose, day, and scheduled time point. At the discretion of the pharmacokinetic scientist and/or biostatistician, samples may be excluded from descriptive statistics if there are large deviations between scheduled and actual sampling times, or large deviations between actual dose and nominal dose.

ISIS 814907 plasma concentration versus time (actual) profiles from Day 1 (MAD and LTE Periods), Day 29 (MAD period), Day 85 up to Day 141 (MAD period), and Day 337 up to Day 421 (LTE period), for each patient, as well as the mean (±SE) plasma concentration versus time (scheduled) profiles by analysis group will be presented graphically on linear and semilogarithmic scales. Additionally, ISIS 814907 plasma concentration versus time (actual) profiles from 0 to 24 hours on Days 1 and 85 (MAD period) and Days 1 and 337 (LTE period) for all patients, as well as the mean (±SE) plasma concentration versus time (scheduled) profiles (0 to 24 hours on Days 1 and 85 [MAD period]; 0 to 24 hours on Days 1 and 337 [LTE period]) for each analysis group will be presented graphically on linear and semilogarithmic scales. Samples may be excluded from the mean plots if there are large deviations between scheduled and actual sampling times, or large deviations between actual dose and nominal dose.

